ANALYTIC PLAN FOR PROTOCOL A Pilot Study of Hypertension Management Using Remote Patient Monitoring Study 1

PRINCIPAL INVESTIGATOR:

[name], MPH
Professor of Medicine, Division of General Internal Medicine & Geriatrics
Director, Center for Primary Care Innovation
[contact]
Email Address: [contact]

VERSION DATE: 1/26/21

Start date 11/19/2020

Define primary study cohort as of this date

Define secondary study cohort as of this date

Define matched control cohort as of this date (attempt to match pilot to control at rate of 4:1 for primary and 2:1 for secondary)

Groups of interest:

- Patients meeting **primary patient population** criteria at the study start date
 - Adults aged 65 to 85 years at the time of the study start date AND
 - One or more office or telehealth visits in the year preceding the study start date at the eligible NM primary care sites AND
 - Medicare or Medicare Advantage insurance on study start date AND
 - Last two office blood pressures elevated (either ≥ 140 mmHg systolic or ≥ 90 mmHg diastolic) in the past 2 years AND
 - Diagnosis of hypertension in the year preceding the study start date (problem list or encounter diagnosis : all of the subcodes of I10, I11, I12, I13, I15) AND
 - Not meet the exclusion criteria
 - Persistent atrial fibrillation as indicated in the EHR
 - Exclude if “permanent atrial fibrillation or persistent atrial fibrillation” [I48.1, I48.2] (active problem list or two encounter diagnoses in past 2 years)
 - Stage IV or more severe kidney disease, defined as the most recent estimated glomerular filtration rate < 30 per $1.73m^2$ or currently on renal replacement therapy (i.e. hemodialysis or peritoneal dialysis) [N18.4, N18.5, N18.6]
 - Diagnosis of dementia as indicated in the electronic health record [all subcodes of F01-F03, all subcodes of G30, all subcodes of G31]
- Patients meeting **secondary patient population** criteria at the study start date
 - Meet criteria for primary population OR
 - Diagnosed hypertension but did not have the last two office blood pressures ≥ 140 mmHg systolic or ≥ 90 mmHg diastolic OR
 - No diagnosis of hypertension in the past year but did have the last office blood pressure ≥ 140 mmHg systolic or ≥ 90 mmHg diastolic

- Control group matched based on the primary study criteria
- Control group matched based on the secondary study criteria.

Matching criteria

- Sex
- Age (+/- 5 years)
- Mean SBP from T-365d to T-183d (+/- 10 mm Hg)

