- Mean SBP from T-182d to T-0d (+/- 10 mm Hg)
- Number of office visits to primary care in the past year categories : 1, 2, 3-4, 5+

Assess for time 0 (11/19/2020)

Characteristics of study populations and matched control populations.

At time 0, 1 month (12/18/2020), 3 months (2/18/2020) and 6 months (5/18/2020) describe for each group:

- The proportion of patients who satisfy the performance measure Controlling High Blood Pressure (NQF 0018)
- The systolic blood pressure at the most recent face-to-face office visit

At time 1 month (12/18/2020), 3 months (2/18/2020) and 6 months (5/18/2020) describe for each group:

- Number of antihypertensive medication intensifications between the study start and the measure date

Hypothesis testing—perform separately for primary and secondary populations

H1: Antihypertensive medication intensification will be greater in pilot clinic(s) with RPM compared to contemporaneous control clinic(s).

Compare at 1, 3, and 6 months the number of medication intensifications between study group and control group using Poisson regression (if variance of medication intensifications is approximately equal to the mean) or otherwise negative binomial regression with study group as the independent variable.

H2: The proportion of patients who satisfy the performance measure Controlling High Blood Pressure (NQF 0018) will be greater in pilot clinic(s) with RPM compared to contemporaneous control clinic(s).

Compare at 1, 3, and 6 months the proportion of patients in the study group and control group who satisfy the performance measure Controlling High Blood Pressure (NQF 0018) using logistic regression with study group and baseline systolic blood pressure as independent variables.

H3: The systolic blood pressure at the most recent office visit will be lower in pilot clinic(s) with RPM compared to contemporaneous control clinic(s).

Compare at 1, 3, and 6 months the systolic blood pressure at the most recent face-to-face office visit among patients in the study group and control group using linear regression with study group and baseline systolic blood pressure as independent variables.

RPM enrolled patient analyses

We will explore the trajectories of blood pressure for individuals who are prescribed RPM.

We will describe all patients who are enrolled in RPM at their enrollment date and follow their blood pressure outcomes at 1, 3, and 6 months from their enrollment (or until the study end date).

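### The top visit-matching band (5+) is unbounded and the H1 model has no covariate, so a difference in visit frequency among frequent attenders can bias the H1 rate ratio in either direction

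*SAP*

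**What the plan says.** Under Matching criteria, the SAP lists five variables: sex, age within 5 years, mean SBP in each of two half-year windows within 10 mm Hg, and "Number of office visits to primary care in the past year categories : 1, 2, 3-4, 5", where the last class is 5+. Bands 1 and 2 are exact, band 3-4 spans a single visit, and only 5+ has no upper limit. The plan is to "attempt to match pilot to control at rate of 4:1 for primary and 2:1 for secondary".

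The H1 outcome is "Number of antihypertensive medication intensifications between the study start and the measure date". It is analysed by Poisson regression, "or otherwise negative binomial regression with study group as the independent variable". H2 is tested "using logistic regression with study group and baseline systolic blood pressure as independent variables" and H3 "using linear regression with study group and baseline systolic blood pressure as independent variables". The visit count enters none of the three models.

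**The concern.** Pilot and control groups are defined by clinic, not by randomisation. By choosing visit frequency as one of five matching variables, the plan treats it as something the groups could differ on and that matters for outcome. In the 5+ band, though, a patient with 5 visits and one with 12 count as an exact match.

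Office visits are a main occasion for intensifying treatment. If the clinics differ in how often they see their frequent attenders, and that pattern carries on after the start date, the H1 count is affected without any effect of remote patient monitoring (RPM). The H1 model has no term that could absorb the difference. The ratio is biased upward if pilot patients attend more often and downward if they attend less often. A clinic-wide pattern does not average out as patients are added, so its effect on the test grows with sample size.

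**Working it through.** The SAP states no sample size, visit distribution or intensification rate, so there is no planned figure to reproduce. What follows is a sensitivity calculation with no RPM effect.

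**Inputs from the SAP:** bands 1, 2, 3-4, 5+; 4:1 matching for the primary population; study group as the only term in H1.

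**Assumed inputs:** prior-year visits follow a negative binomial truncated to 1 or more, with dispersion 2 to 4; bands are matched exactly; the intensification rate is proportional to visits or to their square root; 400 pilot patients, 1,600 controls, 0.5 intensifications per patient, Poisson variance.

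**Step 1: residual ratio after matching.** Give the controls the pilot band shares and compare expected rates:

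RR = Σ(pilot share × pilot band mean) / Σ(pilot share × control band mean).

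Take untruncated means of 4.5 (pilot) and 3.5 (control), dispersion 2, proportional relation:

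| Band | Pilot share | Pilot mean visits | Control mean visits |
|---|---|---|---|
| 1 | 0.145 | 1 | 1 |
| 2 | 0.150 | 2 | 2 |
| 3-4 | 0.259 | 3.464 | 3.443 |
| 5+ | 0.446 | 8.14 | 7.37 |

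- Pilot: 0.145 + 0.300 + 0.897 + 3.630 = 4.972
- Control: 0.145 + 0.300 + 0.892 + 3.287 = 4.624
- RR = 4.972 / 4.624 = 1.075

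Bands 1 and 2 contribute nothing, and the means in band 3-4 differ by less than 1%. Almost all of the residual comes from 5+.

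**Step 2: what matching already removes.** For the same gap the crude proportional ratio is 1.23-1.24. At dispersion 2, log(1.075) / log(1.232) = 0.0723 / 0.2086 = 0.35, so about two thirds of the log bias is gone.

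**Step 3: chance of false support.** SE(log RR) = √(1/(0.5 × 400) + 1/(0.5 × 1,600)) = √(1/200 + 1/800) = 0.0791. One-sided false support = 1 − Φ(1.96 − log RR / SE). For RR = 1.075: 0.0723 / 0.0791 = 0.915, and 1 − Φ(1.045) = 14.8%.

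| Untruncated means, pilot v control | Relation to visits | Matched RR with no RPM effect | False support (nominal 2.5%) |
|---|---|---|---|
| 4.5 v 3.5 | proportional | 1.065-1.075 | 12-15% |
| 4.5 v 3.5 | square root | 1.025-1.028 | 5.0-5.4% |
| 3.5 v 3.0 | proportional | 1.03 | 5.2-6.1% |
| 3.5 v 3.0 | square root | 1.01 | 3.3-3.5% |

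Two variations on 4.5 v 3.5, proportional: with 100 pilot patients the figure is 5.9-6.6%, and with 400 pilot patients and variance twice the mean it is about 8-9.5%. A wider gap, 5.0 v 3.5, gives a matched ratio of 1.04-1.12 across both relations. If pilot patients attend less often, the ratio falls below 1 and true support becomes harder to reach.

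**Step 4: a second set of assumptions.** With control mean parameter 2.5 or 3.5, dispersion 1.5 or 3 and a proportional relation, the matched ratio is 1.01-1.03 if the pilot mean parameter is 10% higher, 1.03-1.07 if 25% higher, and 1.08-1.15 if 50% higher. At 0.3 intensifications per control patient and 300 pilot patients, two-sided rejection is 5.1-5.6%, 5.9-9.0% and 10.1-23.9% in turn, against 5%.

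**Step 5: the remedy.** Fitting the expected rates of Step 1 with study group and log(visits + 1) in a Poisson model brings the 4.5 v 3.5 ratio to 0.99-1.00 under either relation.

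**The case against.** The strongest reply is that the plan already controls visit frequency by matching and that leaving a matched variable out of the outcome model is a common design choice, neither an error nor a contradiction. Most of this stands: in the 4.5 v 3.5 scenario matching does about two thirds of the work. It does not dispose of the point, because the control is incomplete in the one unbounded band. The plan itself adjusts H2 and H3 for baseline SBP after matching on SBP, so adjusting for a matched variable is within its own practice. The planned time-0 description of the groups could reveal an imbalance in visits but would not correct the H1 estimate.

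Four stronger readings are tempting, and the document does not support them:

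- **Pilot patients attend more often.** Nothing in the SAP says or implies this, nor that any booking pattern persists after the start date. No direction of bias is established.
- **Band 3-4 is also too coarse.** It is closed, spans one visit and contributes almost nothing.
- **H2 and H3 are biased in the same way.** The visit count is missing from those models too, but both adjust for baseline SBP, and neither a direction nor a size has been shown for them.
- **The false-positive rate is 12-15%.** That needs a gap of about 29% in untruncated means (4.5 / 3.5 = 1.29), strict proportionality to prior-year visits, 400 pilot patients, 0.5 intensifications each and Poisson variance, all together. Milder combinations give 3-6%.

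**Conclusion.** The point holds for H1 and for the 5+ band. Visit frequency among the most frequent attenders is neither bounded in the matching nor adjusted for in the model, so the H1 rate ratio can be biased either way. For clinic gaps of 3.5 v 3.0 to 4.5 v 3.5, the ratio with no RPM effect is about 1.01 to 1.08, and one-sided false support is about 3-15% against 2.5% at the assumed sample size and event rate. None of these inputs is in the SAP; the figures show what could happen, not what will. The bias is small unless the clinics differ substantially or the cohort is large. This is a minor improvement, worth making because it costs almost nothing.

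**What to change.** Keep the matching as it is. In H1, add the exact number of primary care office visits in the year before the start date to the Poisson or negative binomial model, for example as log(visits + 1). The added 1 matters because the population criteria under Groups of interest allow a patient to qualify through telehealth visits alone; if those are not counted as office visits, the count is zero and log(visits) is undefined. Use pre-start visits only: RPM may change follow-up visits, and adjusting for them could remove part of its effect.

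The count is already needed to form the bands, so the cost is one sentence in the SAP and one degree of freedom in the model.

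### The 3- and 6-month measure dates are printed as 2/18/2020 and 5/18/2020, before the 11/19/2020 start; the year should almost certainly be 2021

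*SAP*

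**What the plan says.** The front matter of the SAP gives "Start date 11/19/2020", and the list of assessments repeats it: "Assess for time 0 (11/19/2020". The document itself is dated "VERSION DATE: 1/26/21".

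Two lists then attach calendar dates to the follow-up points:

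- For the NQF 0018 control measure and for systolic blood pressure (SBP) at the latest face-to-face office visit: "At time 0, 1 month (12/18/2020), 3 months (2/18/2020) and 6 months (5/18/2020) describe for each group".
- For medication intensification: "At time 1 month (12/18/2020), 3 months (2/18/2020) and 6 months (5/18/2020) describe for each group". The quantity reported is "Number of antihypertensive medication intensifications between the study start and the measure date".

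Under the hypothesis-testing heading the time points carry no dates. H1, for example, reads "Compare at 1, 3, and 6 months the number of medication intensifications between study group and control group", and H2 and H3 use the same three time points. The analyses of patients enrolled in remote patient monitoring (RPM) run on each patient's own clock: "at 1, 3, and 6 months from their enrollment (or until the study end date".

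**The concern.** A follow-up date cannot precede the start of follow-up. Both lists place the 3- and 6-month points in the same calendar year as a November start, and so before it. No corrected date appears elsewhere in the SAP.

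The three measures would respond differently if a programmer hard-coded the printed dates:

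- **Intensification count.** The window from study start to measure date would have negative length. That would show itself at once.
- **NQF 0018 status and latest office SBP.** Both look back from an index date. A query run as of 2/18/2020 or 5/18/2020 could return plausible values without any error, and those values would be pre-intervention data labelled as 3- and 6-month results.

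The second case is the one to guard against. Both printed dates also fall inside the earlier of the two periods on which controls are matched for mean SBP. A comparison at those dates would set the groups side by side in a period in which they had been matched, and would say nothing about the effect of RPM.

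**Working it through.** **Inputs, all from the SAP.** Start and time 0: 11/19/2020. Printed follow-up dates: 12/18/2020, 2/18/2020 and 5/18/2020, identical in both lists. Version date: 1/26/21. Earlier SBP matching window: T-365d to T-183d, taking T as time 0.

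**Formula.** Offset in days = measure date − 11/19/2020. Months = days / 30.4375.

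**The plan's own 1-month date.** 12/18/2020 − 11/19/2020 = +29 days = 0.95 months. This agrees with its label and shows the convention: the 18th of the month, one day short of the anniversary of the 19th.

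**The other two dates, as printed and with the year changed:**

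| Label | Date | Offset (days) | Months |
|---|---|---|---|
| 3 months, as printed | 2/18/2020 | −275 | −9.03 |
| 6 months, as printed | 5/18/2020 | −185 | −6.08 |
| 3 months, year 2021 | 2/18/2021 | +91 | +2.99 |
| 6 months, year 2021 | 5/18/2021 | +180 | +5.91 |

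Changing only the year restores both labels and keeps the day-18 convention.

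**Position relative to the matching window.** T-365d is 11/20/2019 and T-183d is 5/20/2020. Both 2/18/2020 and 5/18/2020 lie between them.

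**Position relative to the version date.** 1/26/2021 is day +68. The printed dates were then 68 + 275 = 343 and 68 + 185 = 253 days in the past. The 2021 dates were 91 − 68 = 23 and 180 − 68 = 112 days ahead. This also points to 2021.

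**Extent.**

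- Date entries: 2 lists × 3 follow-up dates = 6, of which 2 × 2 = 4 precede the start.
- Dated follow-up summaries per group: 3 measures (NQF 0018, SBP, intensifications) × 3 time points = 9, of which 3 × 2 = 6 carry a date before the start.

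**The case against.** The strongest reply is that this is a typing slip with only one sensible reading. Each wrong date stands in parentheses after a correct label, time 0 is stated twice, and the 1-month date shows the pattern, so any analyst can recover the intended dates. The hypothesis tests are undated and the RPM-enrolled analyses run from enrollment, so no test is misdated. Because the intensification count shares the same dates, its impossible window would probably expose the mistake before results were used. The counts of affected entries measure how often one wrong year is repeated; they do not measure bias.

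Most of this stands. The intent is clear, no design or model is at fault, and the harm to the tests is conditional. The counts describe extent only, and no effect on an estimate is claimed.

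It does not remove the need to correct the text. These lines specify the outcome measures, and they hold the only calendar dates for two of the three follow-up points, so anyone who needs a cut-off for the population analyses will take it from here. Discovery through the intensification count is likely but not assured, since the NQF 0018 and SBP queries would not fail by themselves.

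**Conclusion.** The concern holds. The 3- and 6-month dates are wrong as printed, by one calendar year, in both places: −275 and −185 days from the start instead of +91 and +180. This affects 4 of 6 follow-up date entries and, if followed literally, 6 of 9 dated follow-up summaries per group. H1 to H3 at 3 and 6 months would be affected only if these dates became their cut-offs. The RPM-enrolled follow-up is unaffected.

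The conclusion that 2021 was meant rests on the month labels, the correct 1-month date and the version date, which all agree. The SAP does not show whether data were later extracted with the printed dates, and nothing here claims that they were. The point should be fixed, but it is no threat to the design.

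**What to change.** In both lists, change the 3-month date to 2/18/2021 and the 6-month date to 5/18/2021, before data extraction. The milestones need no redefinition. If extraction code already exists, check that its cut-offs use 2021.

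The cost is a two-line correction to the SAP, with no change to design, models or data collection. At the version date both corrected time points still lay ahead, so the correction could then have been made before the data for those time points existed.

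### The H1 model rule sets no tolerance for calling the variance equal to the mean and has no suitable branch for variance below the mean; one Poisson model with robust variance would replace it.

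*SAP*

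**What the plan says.** Under Hypothesis testing, H1, the SAP sets this comparison: "Compare at 1, 3, and 6 months the number of medication intensifications between study group and control group". The model is chosen "using Poisson regression (if variance of medication intensifications is approximately equal to the mean) or otherwise negative binomial regression". Study group is the only term: "negative binomial regression with study group as the independent variable".

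The outcome, defined in the descriptive list above the hypotheses, is cumulative: "Number of antihypertensive medication intensifications between the study start and the measure date".

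The hypotheses are tested separately in the primary and secondary populations, so the rule is applied six times (three time points, two populations). The analysis of patients enrolled in RPM borrows the same methods.

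The SAP does not say how close the variance must be to the mean, whether the check is pooled or made within each group, or what happens when the variance is smaller than the mean. It names no robust or scaled variance. It also gives no expected intensification rate, cohort size or significance level.

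**The concern.** There are three weaknesses in the rule as written.

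- **The choice depends on the outcome and has no threshold.** Two analysts with the same data could pick different models, and the six H1 comparisons could end up on different models for no planned reason.
- **The fallback covers a case it cannot handle.** Negative binomial variance is the mean plus a non-negative term, so it can never be below the mean. The rule nevertheless sends every departure from equality to it, in either direction.
- **The intervals rest wholly on the chosen model.** With model-based errors only, a count accepted as Poisson when it is mildly over-dispersed gets an interval that is too narrow. An under-dispersed count gets one that is too wide.

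At stake are the calibration of the H1 confidence intervals and p-values, some power if counts are under-dispersed, and the chance that the planned software returns no standard error and forces an unplanned choice. The rate ratio itself is not at stake: with study group as the only term, both models estimate the ratio of the two group means.

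**Working it through.** **Inputs.** From the SAP: the rule, the single covariate, the three time points, and the matching ratio ("attempt to match pilot to control at rate of 4:1 for primary and 2:1 for secondary", read as controls per pilot patient). The SAP states no figure that could be reproduced. Assumed: two-sided 5% level (H1 is worded directionally, but no level is given); 100 pilot and 400 control patients, with 300 and 1,200 as a second size; independent patients; and the event rates and dispersion values below. Write φ for variance/mean.

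**Formulas** for the log rate ratio, with group sizes n1, n0 and group means m1, m0:

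- Poisson SE = √[1/(n1·m1) + 1/(n0·m0)]
- Negative binomial SE = √[(1/m1 + a)/n1 + (1/m0 + a)/n0], with dispersion a ≥ 0
- Robust SE = √[s1²/(n1·m1²) + s0²/(n0·m0²)], with s² the observed group variance
- True SE = √φ × Poisson SE, so the actual type I error of a Poisson test is 2·[1 − Φ(1.96/√φ)]

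When φ < 1 the best-fitting a is 0, and the negative binomial SE becomes the Poisson SE. Both branches then give the same over-wide interval.

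**Variance below the mean.** If each patient has at most one intensification and a proportion p has one, then φ = 1 − p. With 100 versus 400 patients:

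| p | φ | Poisson SE | True SE | Ratio | Type I error (formula) |
|---|---|---|---|---|---|
| 10% | 0.9 | √(1/10 + 1/40) = 0.354 | 0.335 | 1.05 | 3.9% |
| 20% | 0.8 | √(1/20 + 1/80) = 0.250 | 0.224 | 1.12 | 2.8% |
| 30% | 0.7 | √(1/30 + 1/120) = 0.204 | 0.171 | 1.20 | 1.9% |

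Simulation agrees at 20 and 30% (about 2.7 to 2.8% and 1.8%), where robust variance gives about 4.7 to 5.0%. At 10% the simulated 3.3% is partly a small-sample effect, since robust variance itself gives 4.3% there. A correctly calibrated test with 80% power would have Φ(2.80 − 1.96/√φ) under the over-wide SE: about 73% at p = 20% and 68% at p = 30%.

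**Does negative binomial return a result?** In 200 fits with at most one event per patient (mean 0.3) and 200 with at most two (mean 0.6), both with φ = 0.7, all 400 converged to the Poisson rate ratio. The SE was missing in 100% of the first set and 5.5% of the second; otherwise it equalled the Poisson SE. Further 0/1 fits in the same package showed that this depends on the optimiser. One setting failed to converge in 60 of 60 datasets at each event rate. Another converged in 60 of 60 with the SE missing in all. A third lost the SE in 38 to 52 of 60.

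**Variance above the mean.** If Poisson is always kept:

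| φ | Poisson SE / true SE | Type I error |
|---|---|---|
| 1.1 | 0.953 | 6.2% |
| 1.2 | 0.913 | 7.4% |
| 1.3 | 0.877 | 8.6% |

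The rule does not always keep Poisson. It was simulated in full with no group effect: 2,000 trials per scenario, means 0.3 and 0.8, both cohort sizes, and Poisson kept when the pooled φ fell within 0.8 to 1.2. Monte Carlo error is about 0.5 points.

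| True φ | Type I error of the full rule |
|---|---|
| 0.7 | 1.6–2.4% |
| 1.1 | 5.6–6.4% |
| 1.2 | 5.0–6.9% |
| 1.3 | 4.9–6.4% |
| 1.5 | 4.5–5.1% |

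One run with a wider tolerance (0.7 to 1.3) gave 6.6% at φ = 1.3.

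**The alternative.** Poisson with robust variance and no dispersion check gave 4.1 to 6.2% over all 27 scenarios, and 4.1 to 5.0% at φ = 0.7.

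**The case against.** Choosing between Poisson and negative binomial by dispersion is common practice, this is a pilot, and the realistic effect is a shift of one or two points in type I error or a modestly conservative interval. That is fair as to size. It does not supply a branch for variance below the mean or a tolerance.

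Four stronger readings are tempting, and the documents do not support them.

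- *Negative binomial cannot be fitted to under-dispersed counts.* It can: the dispersion goes to its zero bound and the Poisson estimate comes back. Non-convergence appears under some optimiser settings only. What can be lost is the standard error.
- *One-month counts will be under-dispersed because they are mostly 0 or 1.* This does not follow. A Poisson count with mean 0.1 is 0 or 1 in 99.5% of patients and has φ = 1. A split of 90/8/2% over 0, 1 and 2 events has mean 0.12 and variance 0.16 − 0.0144 = 0.1456, so φ = 1.21. Under-dispersion needs almost no patient with two events, and the SAP gives no rate from which to judge.
- *Type I error under the rule is 6.2 to 8.6%.* Those figures hold only if Poisson is kept whatever the variance. The planned switch to negative binomial removes most of the excess.
- *The H1 model must also be clustered.* H1 to H3 name no clustering, and the wording allows a single pilot clinic, where a clinic-clustered sandwich variance would be unreliable. That is a separate question.

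It is also true that at 10% events (φ = 0.9) most analysts would stay with Poisson and never reach the fallback. At 20% the choice is borderline. Either way the interval is the same, so the branch matters only for whether an SE is returned.

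**Conclusion.** The concern holds, at modest size. The rule is incompletely fixed, because the tolerance and the pooling of the check are undefined. It is also wrong in one branch, because it assigns variance below the mean to a model that cannot represent it.

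The consequences run in opposite directions. With 0/1 counts and 20 to 30% of patients intensified, intervals are about 12 to 20% too wide and type I error is about 2.8 to 1.8%, with an SE that some software will not return. At 10% or less the effect of dispersion is small. With variance/mean of 1.1 to 1.3 and a 0.8 to 1.2 tolerance, type I error is about 5 to 6%, at most about 7%.

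A reader might infer that the rule gives wrong intervals in general. It does not: when the variance equals the mean, or clearly exceeds it and negative binomial is used, calibration is close to nominal. Cohort sizes, event rates, dispersion, tolerance and significance level are all assumptions, since the SAP states none of them, and patients were treated as independent.

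**What to change.** Delete the variance-based switch and prespecify one model for H1 at 1, 3 and 6 months in both populations: log-link Poisson regression on study group with robust (sandwich) variance, and no dispersion check used to choose the model. State that the RPM-enrolled comparisons use the same model. The observed variance/mean can still be reported descriptively.

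The estimate remains the rate ratio that the SAP already targets. The cost is one sentence in the SAP and one software option, with no extra data. Whether the variance should also allow for clinic or matched set should be settled separately.

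### H2 leaves time-0 NQF 0018 status out of its logistic model although the SAP records it, which costs some power in the secondary population

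*SAP*

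**What the plan says.** Under H2 the SAP says: "Compare at 1, 3, and 6 months the proportion of patients in the study group and control group who satisfy the performance measure", with the analysis done "using logistic regression with study group and baseline systolic blood pressure as independent variables". The descriptive section before it lists the same measure among the items to be reported by group, starting at time 0: "At time 0, 1 month (12/18/2020), 3 months (2/18/2020) and 6 months (5/18/2020) describe for each group". (The years printed for the later dates play no part in this point.)

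The tests are to be run in both populations: "Hypothesis testing—perform separately for primary and secondary populations". The two differ in how far control can vary at time 0. Primary patients must satisfy "Last two office blood pressures elevated (either ≥ 140 mmHg systolic or ≥ 90 mmHg diastolic) in the past 2 years AND". The secondary population adds patients described by "Diagnosed hypertension but did not have the last two office blood pressures ≥ 140 mmHg systolic or ≥ 90 mmHg diastolic OR", and also undiagnosed patients whose last reading was elevated.

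The matching criteria are sex, age, mean SBP in two half-year windows (each within 10 mm Hg) and number of primary care visits. Neither NQF 0018 status nor diastolic pressure is among them. The SAP does not say which reading or average counts as baseline SBP in the H2 and H3 models.

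**The concern.** H3 adjusts for the baseline value of its own outcome. H2 adjusts for a related measure and leaves out its own baseline, although that value is already to be extracted. Three features suggest that one linear SBP term does not carry all the information:

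- Status changes abruptly at a threshold. A matched pair with mean SBP of 135 and 145 lies within the 10 mm Hg tolerance and on opposite sides of 140.
- Diastolic elevation alone counts as elevated in the SAP's own criteria, yet diastolic pressure is neither matched on nor modelled.
- The 1-month date, 12/18/2020, is 29 days after the 11/19/2020 start. If few patients have a new reading by then, and the earlier reading stands for the rest, time-0 status largely determines the 1-month outcome.

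At stake is the power of H2 in the secondary population, mainly at 1 month. In the primary population the last reading is elevated by definition, so time-0 status should be constant or nearly so and the point hardly applies.

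**Working it through.** The SAP states no sample size, control rate, SD, effect size or re-measurement rate, so there is no figure of its own to reproduce. The size was found by simulating the secondary population.

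**From the SAP:** two controls per pilot patient; the planned covariates; elevation thresholds of 140 and 90.

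**Assumed:** 300 pilot and 600 control patients; SBP mean 138 (between-patient SD 13, within-patient SD 11); DBP mean 77 or 84 (SDs 8 and 7); correlation 0.5; control = SBP below 140 and DBP below 90; true SBP effect 4 mm Hg; two-sided 0.05. A given share of patients has a new reading and the others keep their earlier status. There were 1500 replicates.

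**Comparison:** model A is the planned one (group, baseline SBP). Model B adds time-0 status. Relative efficiency = (mean z in B / mean z in A)². A ratio of 1.45 means that model A needs about 45% more patients for the same power.

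| Baseline SBP; DBP mean | Re-measured | Mean z, A → B | Power, A → B | Ratio |
|---|---|---|---|---|
| Last reading; 77 | 30% | 1.14 → 1.37 | 0.20 → 0.28 | 1.45 |
| Last reading; 77 | 60% | 1.99 → 2.08 | 0.52 → 0.54 | 1.09 |
| Last reading; 77 | 85% | 2.57 → 2.59 | 0.745 → 0.749 | 1.02 |
| Last reading; 77 | 100% | 2.93 → 2.93 | 0.84 → 0.84 | 1.00 |
| Mean of two; 77 | 30% | 1.04 → 1.37 | 0.17 → 0.28 | 1.74 |
| Mean of two; 77 | 60% | 1.99 → 2.13 | 0.50 → 0.58 | 1.15 |
| Last reading; 84 | 30% | 1.04 → 1.36 | 0.19 → 0.28 | 1.70 |
| Last reading; 84 | 60% | 1.88 → 2.04 | 0.47 → 0.55 | 1.18 |

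Ratios come from unrounded z values; for the first row the rounded values give (1.37/1.14)² = 1.44.

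Other sample sizes agree. With 600 and 1200 patients the ratios were 1.57, 1.17 and 1.04 at 30%, 55% and 80% re-measured (last reading), and 1.79, 1.23 and 1.05 (six-month mean). With 400 and 800 they were 1.56-1.80 at 30%, about 1.2 at 55%, 1.06 at 80% and 1.01 at 100%, with type I error near 5%.

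The gain is in power, not in a smaller standard error. In the first row the SE of the log odds ratio rises from 0.206 to 0.251, but the conditional log odds ratio rises more, from 0.235 to 0.344.

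**Imbalance, no true effect.** Two kinds were tried.

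1. *Different time-0 status at equal mean SBP, with baseline SBP a mean.* With 600 and 1200 patients and a 4.5-point difference in time-0 control, model A gives odds ratios of 1.22, 1.12 and 1.05 at 30%, 55% and 80% re-measured, with false-positive rates of 37%, 16% and 7%. Model B gives 0.99-1.00 and 4-6%. If baseline SBP is the last reading, model B gains power only.
2. *Persistently lower pressure in the pilot group (SBP and DBP both by 2 mm Hg, time-0 control about 5 points higher), with 300 and 600 patients.* The bias is 0.10-0.14 on the log odds scale in both models. Rejection is 0.06-0.14 in A and 0.08-0.15 in B, so the added term does not help.

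**The case against.** The case for leaving H2 alone has weight. The model already contains SBP, the main continuous component of the outcome, and controls are matched on mean SBP in two windows. With DBP mean 77, SBP below 140 and full control status disagreed in only about 2% of simulated patients. The material gains need the carry-forward assumption, which the SAP does not state for NQF 0018: it refers to the latest visit only for SBP. The measure's threshold and its handling of missing readings lie in an outside specification. All this stands, and it limits the point to a refinement. If only 30% were re-measured, 70% of outcomes would also predate the intervention, and no covariate repairs that.

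A further objection is that a near-deterministic covariate could bring the logistic fit close to separation. It does not stand: no convergence failure occurred even with 15% re-measured.

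A reader might infer something stronger, namely that H2 lacks baseline adjustment or is biased by imbalance in control status. The SAP does not support that. The only individual SBP value it lists at time 0 is the one from the latest in-person office visit, and on that reading the added term gives power but no protection against bias. The bias figures need baseline SBP to be a mean, and also an imbalance that the SAP neither states nor implies. Persistent differences in pressure between the groups remain with or without the term.

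**Conclusion.** The point holds as a minor one. H2 omits a baseline value that the SAP already extracts, that varies by design in the secondary population and that is not matched on. The cost is power there: a squared z ratio of about 1.45-1.8 if 30% of patients are re-measured, 1.1-1.2 at 55-60%, and 1.00-1.06 at 80% or more. These figures assume carry-forward of earlier status, control below 140/90, and the simulated means and SDs. The direction was the same in every set-up; the size depends mostly on the re-measurement rate, which the SAP does not give. Protection against imbalance is a conditional extra and should not be the reason for the change. H2 is not invalid as written.

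**What to change.** In the secondary population, fit H2 with three covariates: the pilot/control indicator, baseline SBP, and time-0 NQF 0018 status (yes/no). State that baseline SBP is the most recent office reading at time 0. In the primary population, omit the status term if it is constant there.

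The change takes a line or two of SAP text and no new data. It has a small price: one degree of freedom, and a secondary-population odds ratio that is conditional on time-0 status. Because odds ratios are non-collapsible, that value is not directly comparable with the primary-population odds ratio, and the SAP should say so.
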